## 1.0 OBJECTIVES

### 1.1. Primary Objective

To examine the efficacy of an eHealth intervention for improving symptoms of insomnia among adult survivors of childhood cancer.

Hypothesis 1.1.a.: Survivors randomized to an eHealth CBTi intervention will report significantly fewer symptoms of insomnia post-intervention compared to survivors randomized to online patient education only.

### 1.2. Secondary Objectives

1.2.1. To examine the impact of an eHealth intervention for insomnia on the clinical severity of insomnia symptoms in adult survivors of childhood cancer.

Hypothesis 1.2.1.: A larger proportion of survivors randomized to the CBTi intervention will no longer meet clinical criteria for insomnia post-intervention compared to survivors randomized to online patient education.

1.2.2. To determine whether treatment of insomnia symptoms will improve neurocognitive function in adult survivors of childhood cancer with both insomnia and neurocognitive impairment.

Hypothesis 1.2.2.a.: Survivors randomized to an eHealth CBTi intervention will report significantly fewer symptoms of neurocognitive impairment post-intervention compared to survivors randomized to online patient education only.

Hypothesis 1.2.2.b.: Improvement in insomnia symptoms will mediate the association between intervention status (CBTi vs. online patient education) and improved neurocognitive function post-intervention.

Hypothesis 1.2.2.c.: Symptoms of emotional distress and cardiac health will be associated with improved insomnia symptoms and neurocognitive function.

1.2.3. To explore the mediating effects of improved neurocognitive function, emotional distress, and cardiovascular health on the association between insomnia symptoms and quality of life.

Hypothesis 1.2.3.a.: Survivors with improved insomnia symptoms following completion of an eHealth CBTi intervention will report better health-related quality of life compared to survivors without improved insomnia symptoms.

Hypothesis 1.2.3.b.: Neurocognitive function, symptoms of emotional distress, and biomarkers of cardiovascular health following completion of the eHealth CBTi intervention will mediate the association between improved insomnia symptoms and quality of life 6-months post-intervention.

## 2.0 BACKGROUND AND RATIONALE

### 2.1. Background

**Childhood Cancer Survivors Are a Growing Population with a High Burden of Morbidity** - More than 80% of children diagnosed with a new cancer now survive five years, with most becoming long-term survivors. This has resulted in a growing population of childhood cancer survivors, estimated to approach half a million by 2020. Unfortunately, curative treatments also result in toxicities that leave many survivors with substantial burden of adverse physical and mental health outcomes. Morbidities commonly observed after cancer treatment include fatigue and sleep disturbance, neurocognitive impairment, emotional distress, cardiovascular disease, and diminished quality of life (QoL).

Defined as difficulty initiating or maintaining sleep, or nonrestorative sleep resulting in decreased daytime function, insomnia is the most commonly reported sleep disturbance among adults. In the general population, rates of insomnia range from 10 to 15%, with higher prevalence observed among women than men. Insomnia also impacts a substantial proportion of childhood cancer survivors. A recent report indicated that 28% of adult survivors of childhood cancer (excluding CNS tumor survivors) experience symptoms severe enough to warrant active treatment for insomnia. Compared to siblings, adult survivors of childhood cancer are significantly more likely to report poor sleep efficiency (PR=1.3; 95% CI, 1.-1.5), with one-third reporting delayed onset and less than 7 hours of sleep per night. Notably, sleep disturbances following treatment for childhood cancer are often present in adolescence and likely persist for decades into adult survivorship. It has been recently reported that approximately two-thirds of adolescent survivors of acute lymphoblastic leukemia (ALL) experience delayed sleep onset and 30-40% had frequent nighttime and premature awakenings. Insomnia has been associated with many of the late health complications observed in survivors of childhood cancer, including neurocognitive impairment, emotional distress, and cardiovascular disease. Because adult survivors of childhood cancer have been exposed to neurotoxic and cardiotoxic chemotherapies and radiation, their compromised cardiovascular and neurologic systems may be more sensitive to the effects of insomnia on neurocognitive and cardiac functions. Thus, there is not only a need

for a widely available therapy to treat insomnia, but there is also a need to understand how improved insomnia symptoms impact neurocognitive function and late health morbidities in childhood cancer survivors.

## 2.2. Rationale

### Insomnia and Neurocognitive Morbidity

In non-cancer populations, insomnia has been associated with impaired cognitive performance, particularly in the domains of attention, memory, and executive function. A recent meta-analysis revealed moderate effects sizes for the impact of insomnia on episodic memory (ES = -0.51), problem solving (-0.42), and working memory (ES = -0.42). Working memory impairment has been observed on direct performance-based measures as well as through assessment of neural function via integrity of the hippocampus in adults with insomnia. Insomnia also has been associated with dementia in the general population and emerging evidence suggests that adult survivors of childhood cancer may experience accelerated cognitive aging. Using data from the Childhood Cancer Survivor Study (CCSS), we demonstrated that among adult survivors (n=1,426), after adjustment for neurotoxic therapies [e.g., cranial radiation], poor sleep quality is associated with impaired task efficiency (RR=1.23, 1.01-1.49) and memory (RR=1.45, 1.19-1.76); daytime sleepiness is associated with emotional regulation problems (RR=1.38, 1.14-1.67), diminished organization (RR=1.80, 1.31-2.48), and impaired memory (RR=2.05, 1.63-2.58). There are no data to suggest that neurocognitive deficits precede the onset of insomnia symptoms; however, sleep distribution has been shown to exacerbate neurocognitive deficits.

### Insomnia and Psychiatric Morbidity

Insomnia is highly comorbid with a range of psychiatric disorders. Comorbidity estimates range between 30% and 50% with depression and anxiety being among the most highly comorbid conditions. Though temporal relations are difficult to confirm, insomnia has repeatedly been shown to be a clinical predictor of subsequent depression. Recent path analyses suggest that sleep problems cause significantly more dysphoria than dysphoria causes sleep problems. Among survivors enrolled in the CCSS, we have shown that survivors with elevated depressive symptoms are four times more likely to report disrupted sleep, including symptoms of insomnia (OR, 4.4; 95% CI, 3.1 to 6.3).

### Insomnia and Cardiovascular Morbidity and Mortality

In the general population, insomnia is associated with cardiovascular disease, including risk of myocardial infarction, coronary heart disease, and stroke as well as increased risk of cardiopulmonary mortality. Furthermore, chronic insomnia has been shown to be an independent risk factor for new onset hypertension, even when controlling for other risk factors including smoking, alcohol consumption, depression, race, diabetes, and obesity. Elevated resting heart rate, lower heart rate variability, and poorer cardiorespiratory fitness have been observed among adults with insomnia. Insomnia also has been associated with dyslipidemia and hypercholesterolemia. In a recent meta-

St. Jude Children's Research Hospital

IRB NUMBER: 19-0121

IRB APPROVAL DATE: 05/04/2021

[figure not shown]
analysis, sleep disturbance was significantly associated with increased inflammation (i.e. levels of C-reactive protein [CRP] and interleukin-6 [IL-6]). Among survivors of ALL we have demonstrated associations between symptoms of insomnia and worse neurocognitive function as well as higher levels of IL-6, IL-1 $\beta$ , and high sensitivity CRP and worse performance on measures of executive function and processing speed. These data suggest a link between sleep, systemic inflammation, and neurocognitive function in survivors. Moreover, in survivors of childhood cancer, systemic inflammation has been implicated as promoting development of cardiovascular disease. Because symptoms of insomnia are often present many years before the onset of cardiac disease in survivors of childhood cancer, we hypothesize that these symptoms temporally precede cardiovascular morbidity observed in adult survivors.

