### **3.2. Exclusion Criteria**

- 3.2.1. History of a brain tumor
- 3.2.2. An irregular schedule that would prevent adoption of intervention strategies (i.e. work schedule resulting in usual bedtime earlier than 8 PM or later than 2 AM or arising time earlier than 4 AM or later than 10 AM)
- 3.2.3. Currently pregnant or breast feeding
- 3.2.4. Behavioral treatment for insomnia in the past 12 months
- 3.2.5. Diagnosis of a schizophrenia or psychotic disorder
- 3.2.6. Alcohol or drug abuse in past year
  - 3.2.6.1. Per exclusion criteria 3.2.6., The Alcohol Use Disorders Identification Test (AUDIT) will be used to screen for individuals who have active alcohol use disorders and the Drug Abuse Screen Test (DAST-10) will be used to screen for individuals with drug abuse. Both questionnaires include 10 items and are well-validated.
- 3.2.7. Other concurrent sleep disorders, including narcolepsy, obstructive/central sleep apnea, or restless leg syndrome
- 3.2.8. Current treatment or intervention for cognitive impairment (i.e. stimulant medication, transcranial direct current stimulation)

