## Cardiovascular Health Indices

1) Using the Dried Blood Spot (DBS) method, blood will be collected to measure:

- a. **serum biomarkers of inflammation:** interleukin [IL] IL 6, high sensitivity C reactive protein [hsCRP]
- b. **oxidative stress:** myeloperoxidase
- c. **lipid profile:** triglycerides, total Cholesterol, HDL Cholesterol

We will mail the participants a Dried Blood Spot (DBS) Kit, including written directions and a link to a video that explains the procedure in detail [<https://bcove.video/2LixHlr>]. Participants will collect about six drops of blood by pricking their finger. The 6 blood drops usually required to fill a specimen card are equal to a total blood volume of about ¼ teaspoon and the collection of a dried blood spot sample usually takes about 10 minutes. The samples will be shipped to St. Jude Children's Hospital, where they will be stored until the end of the study. At the end of the study, the Dried Blood Spot (DBS) cards will be shipped to the University of Washington for analysis. All samples will be assayed in duplicate and the average of the two measures will be used for data analyses. All samples from individual participants will be run on the same assay plate to reduce intra-assay variation. Serum biomarkers will be measured at baseline, post-intervention, and 6-month follow-up.

St. Jude Children's Research Hospital

IRB NUMBER: 19-0121

IRB APPROVAL DATE: 05/04/2021

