2) Resting Heart Rate (RHR) and Heart Rate Variability (HRV) will be measured by having participants wear the WHOOP wrist monitor. We will use a time domain measure of heart rate variability (HRV), a non-invasive, albeit indirect way to investigate autonomic nervous system function. It is attractive in this large cohort study, with participants distributed around North America, because today's sensor technology allows remote collection of data in participants usual environments while doing their usual activities. We will use the WHOOP® strap wearable biosensor to obtain standard deviation of NN (normal to normal RR) intervals (SDNN) measured over a 24-hour period and recorded in milliseconds (ms). SDNN captures total HRV; low values over a 24-hour period indicate lack of circadian rhythm. We selected this measure as our primary outcome because of its documented associations with morbidity and mortality in several large studies. Data from the Framingham Heart Study (N=2501) indicate that a one standard deviation decrement in the SDNN (log transformed), captured remotely over 2 hours, is associated with a nearly 50% increased risk (HR 1.47, 95% CI 1.16-1.86) of new onset cardiac conditions, even after accounting for other known risk factors for autonomic dysfunction. In addition, among persons with congestive heart failure (UK-heart, N=433), in adjusted models, a 41.2ms decrement in SDNN, measured over 24-hours, was associated with a 1.62 (95% CI 1.16-2.44) increased risk for all-cause mortality, and the strongest predictor of death related to progressive heart failure. The WHOOP device includes a photoplethysmography-based heart rate/heart rate variability sensor, an accelerometer, and sensors to detect ambient temperature and galvanic skin response. For this study participants with 24-hour SDNN <50ms will be classified with unhealthy HRV, those with values 50-100ms with compromised HRV, and those with values >100ms with normal HRV. The participants will wear the WHOOP wrist monitor for a period of 7 to 11 consecutive days at three specified intervals [baseline, post-intervention, 6 months]. The mailing of WHOOP wrist monitors will be coordinated by study personnel at St. Jude in collaboration with the CCSS coordinating center. Participants will receive a WHOOP wrist monitor along with a pre-paid return package. The WHOOP wrist monitor will be mailed to the participant at baseline and maintained by the participant for the duration of the study. Heart rate data will be uploaded by participants using their smart phone or tablet to a secure cloud-based platform hosted by WHOOP and securely accessible by the study team at St. Jude

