direct relationships between change in ISI (baseline to post-intervention) with emotional distress and cardiac health indices at postintervention time points and with HRQoL measures. To establish whether a mediation relationship exists, we will follow standard methodology by 1) establishing that there is an association between the causal variable (e.g. CBTi intervention) and the outcome (e.g. neurocognitive impairment), 2) establishing the association between the causal variable and the mediator and 3) showing that the mediator is associated with the outcome variable in a model with the causal variable included and 4) in the same model as used to evaluate step 3, determine that the relationship between the causal variable and the outcome variable is attenuated by inclusion of the mediator in the model. We do not expect to observe complete mediation in any of our investigations. Specifically, the above methodology will be used to test hypothesis 1.2.2.b with the causal variable defined as CBTi intervention, mediator as change in insomnia (ISI) and outcomes as neurocognitive indices. Hypothesis 1.2.2.c will consider change in insomnia as the causal variable, neurocognitive function indices, emotional distress symptoms and cardiovascular risk indices as mediators for the outcome HRQoL at 6 months. In addition to the stepwise model-based approach outlined above, we will also evaluate relationships using Structural Equation Modelling (SEM) approaches to evaluating mediation, which would allow simultaneous evaluation of the multiple pathways and classes of variables together in a single model, with improved power, allowing estimates of direct and indirect effects calculated from each. All effects size estimates (mean differences and/or odds ratios) will be presented along with associated confidence intervals and two-sided p-values, both unadjusted and adjusted for multiple comparisons. Primary therapies for childhood cancer have been associated with insomnia and study outcomes (neurocognitive morbidities, emotional distress, cardiovascular risk). Because our study inclusion criteria require that survivors have observed neurocognitive deficits we do not expect differential responses to SHUTi by previous childhood cancer treatment exposures. However, chemotherapy exposures and radiation doses are abstracted from medical records and cumulative doses of methotrexate (high dose and intrathecal), cytarabine, and cranial radiation will be included as covariates in relevant analyses. In addition, we will conduct sensitivity analyses to examine their contributions to treatment response.

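### The paths from change in ISI to the cardiovascular indices, and from those indices to quality of life, are open to confounding: the plan names no source for smoking, diabetes, BMI or cardiometabolic medication and adjusts for none of them

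*Combined protocol and SAP*

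**What the plan says.** Hypothesis 1.2.3.b (section 1.2) is that "biomarkers of cardiovascular health following completion of the eHealth CBTi intervention will mediate the association between improved insomnia symptoms and quality of life", with HRQoL taken 6 months after the intervention; neurocognitive function and emotional distress are proposed as mediators alongside. Section 9.1 refers to "direct relationships between change in ISI (baseline to post-intervention) with emotional distress and cardiac health indices at postintervention time points". It then describes a four-step mediation procedure plus structural equation modelling (SEM), with change in insomnia as the causal variable and HRQoL at 6 months as the outcome. Section 9.1 gives this analysis the label 1.2.2.c, although its content matches 1.2.3.b.

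The cardiovascular part of the Rationale (section 2.2) reports one cited result on hypertension as holding "even when controlling for other risk factors including smoking, alcohol consumption, depression, race, diabetes, and obesity". The words describe how that study was adjusted.

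The indices are set out in section 4.3, Cardiovascular Health Indices. From dried blood spots come IL-6, hsCRP, myeloperoxidase and a lipid profile ("triglycerides, total Cholesterol, HDL Cholesterol"). From the wearable, "Resting Heart Rate (RHR) and Heart Rate Variability (HRV) will be measured by having participants wear the WHOOP wrist monitor".

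Two sets of covariates are named in section 9.1. The primary model uses the stratification factors, which section 3.5 lists as sex, age group and cranial radiation. Other relevant analyses use cumulative methotrexate, cytarabine and cranial radiation doses. Adjustment for unnamed characteristics is also allowed if the arms turn out unbalanced.

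Neither the table in section 5.2 nor Appendix I has a row for smoking, diabetes, height, weight or medication, and the blood panel has no glycaemic marker. On alcohol, section 3.2.6.1 says: "The Alcohol Use Disorders Identification Test (AUDIT) will be used to screen for individuals who have active alcohol use disorders". No other use of the score is stated.

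**The concern.** Randomisation balances the arms. It does not balance people whose ISI improved against people whose ISI did not, nor people with high against low HRV or lipids. A participant who smokes, is obese or has diabetes may have worse cardiovascular indices and lower quality of life, and may respond less well to treatment. Medication acting on lipids, heart rate or blood pressure can shift the indices directly. An analysis without these variables could credit cardiovascular health as a route from insomnia to quality of life when a shared cause explains the association.

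The plan already reasons this way for one class of variable. Section 9.1 notes that cancer therapies are related both to insomnia and to the study outcomes, and adjusts for their doses. It does not extend the argument to lifestyle or cardiometabolic factors. If those variables are neither collected nor retrieved, the question cannot be examined later.

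**Working it through.** The plan states no figure for these paths, so there is nothing of its own to reproduce. The check has two parts.

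**1. What is covered**

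| Factor | Trial schedule | Other source named | Covariate in 9.1 |
|---|---|---|---|
| Smoking | no | no | no |
| Diabetes | no | no | no |
| Height/weight, BMI | no | no | no |
| Lipid-lowering, beta-blocking or blood-pressure drugs | no | no | no |
| Alcohol | AUDIT, baseline | not needed | no (screening only) |
| Cancer-therapy doses | no | medical records | yes |
| Baseline cardiovascular index, baseline HRQoL | yes | not needed | not stated for these paths |

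The allowance for adjusted comparisons does not fill the gap. It is triggered by imbalance between arms, which is a different problem.

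**2. How large the bias could be**

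Inputs from the documents: 280 participants at 6 months (protocol summary, Evaluation); about 70 per sex per arm, so 2 x 70 = 140 per sex (Power and sample size); two-sided 0.05. Assumed, because the documents give no value: one unmeasured confounder with standardised links a to the index and b to HRQoL, and no true effect of index on HRQoL.

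- Spurious correlation: r = a x b.
- Test statistic centre: d = atanh(r) x sqrt(n - 3).
- False-positive rate: Phi(d - 1.96) + Phi(-d - 1.96).

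For n = 280 and a = b = 0.3: r = 0.09, atanh(r) = 0.0902, sqrt(277) = 16.64, d = 1.50. The rate is Phi(-0.458) + Phi(-3.46) = 0.3235 + 0.0003 = 32.4%.

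| a, b | r | n = 280 | n = 140 |
|---|---|---|---|
| 0.1, 0.1 | 0.01 | 5.3% | 5.2% |
| 0.2, 0.2 | 0.04 | 10.2% | 7.5% |
| 0.2, 0.3 | 0.06 | 17.0% | 10.8% |
| 0.3, 0.3 | 0.09 | 32.4% | 18.4% |
| 0.3, 0.4 | 0.12 | 51.9% | 29.2% |

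Simulation of the 0.3 x 0.3 case at n = 280 gives about 31%, and about 5% once the confounder is in the model.

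These are rates for one leg. The stepwise procedure also requires ISI change to be associated with HRQoL and with the index. At n = 280 with 0.3 x 0.3 links:

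- If ISI change has no true effect on either, all three associations are significant in about 1% of simulated trials (0.2% to 3.1% as the confounder's assumed link to ISI change goes from 0.1 to 0.3).
- If ISI change truly affects both index and HRQoL, the first two steps are nearly always met and the rate returns to about 30%, close to the single-leg figure.

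The second case matters because it is close to what the trial hypothesises: insomnia improvement helps both, and the open question is whether one runs through the other.

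**The case against.** Several points on the other side have force.

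- A reader might infer from the Rationale that the protocol itself requires control for smoking, alcohol, diabetes and obesity. It does not. The sentence reports a general-population finding that "chronic insomnia has been shown to be an independent risk factor for new onset hypertension", with that study's adjustment set. Blood pressure is not an index in this trial. The HRV evidence in section 4.3 is described as holding "even after accounting for other known risk factors for autonomic dysfunction", with none of the four factors named. The point rests on the schedules and section 9.1, not on the Rationale.
- A reader might infer that the data cannot be had. Absence from the schedule does not show that: cancer-therapy doses are not in the schedule either. The trial is nested in CCSS and says it will use CCSS resources. The documents do not say whether CCSS holds these variables, and nothing requires their use.
- In the text available for this review, the sentence introducing the ISI-change models is cut at its start, so a covariate statement there cannot be excluded. The later covariate sentence is intact and lists cancer therapies only.
- The exposure is within-person change, so stable traits bias the ISI-to-index leg only if they predict response. That stands. It does not protect the index-to-HRQoL leg, where no baseline adjustment is stated.
- Past-year alcohol or drug abuse and sleep apnoea are exclusions, and depressive symptoms are measured with the PHQ-9. This narrows the problem but leaves smoking, diabetes, BMI and medication.
- Objective 1.2.3 is worded as exploratory, which limits the consequences. It does not make the estimates interpretable as mediation.

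**Conclusion.** The concern holds as a gap in secondary analyses. The non-randomised cardiovascular paths, mainly index to HRQoL, are open to confounding by common factors that the visible plan neither sources nor adjusts for. To say that the paths are confounded would go too far: direction and size are unknown, and with weak links (0.1 x 0.1) the effect is negligible.

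At n = 280 the single-leg false-positive rate is about 5% to 52% across the assumed links. A reader might take 32% as the chance of a false mediation claim. It is not. The full stepwise rate is about 1% when ISI change has no true effects and approaches the single-leg rate only when ISI change truly affects both index and HRQoL. All these figures rest on one assumed confounder and on links that the documents do not give.

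The primary ISI comparison is unaffected. So are all between-arm comparisons, including those on the cardiovascular indices, which randomisation protects apart from attrition.

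**What to change.** 1. Name a source for baseline height and weight, current smoking, diabetes, and current lipid-lowering, beta-blocking or blood-pressure medication (yes/no). Use recent CCSS records where they exist, otherwise a short baseline form in RICE.
2. In section 9.1, pre-specify these variables, the baseline AUDIT score, the baseline value of the cardiovascular index and baseline HRQoL as covariates in every model from ISI change to a cardiovascular index and from an index to HRQoL, including the SEM. The last three are already collected. In a simulation assuming a weight of 0.5 to 0.7 on the baseline value, adjusting for the baseline index alone reduced the 0.3 x 0.3 single-leg rate from about 32% to 9-13%.
3. Add a sensitivity analysis for unmeasured mediator-outcome confounding, and report these paths as associations.

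The cost is a few baseline items, a few degrees of freedom and a short addition to section 9.1. Participants already past baseline would need CCSS-filled values or one retrospective question set, which are less reliable than values taken at baseline. Between-arm analyses need no change.
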